4.2 Dispensing Clinical Trial Material (CTM) Kits

All subjects in the study will receive open label M207, 3.8 mg to administer as two 1.9 mg patches to treat each qualified migraine during the study.

There are two types of M207 kits for each subject, starter kits and refill kits, clearly labeled and visually distinguishable. Each M207 CTM kit includes either 4 (starter kit) or 8 (refill kit) individual foil pouches or cups. Each pouch or cup contains one patch. The starter kit dispensed on day 1 contains the applicator. Refill kits will be dispensed as needed throughout the study. A replacement applicator will be issued at approximately six months, and or/as needed if a previously dispensed applicator is defective or lost.

Zosano may employ an electronic system for supply management of clinical trial material (CTM) kits. The CTM system, if employed, is for drug supply management purposes only. There is no drug randomization as drug assignment is open-label.

At each medication dispensation visit, after it has been established that a subject continues to qualify for the study, study staff will document the total number of patches dispensed to each subject and unopened (unused) patches returned at each visit in the eCRF and drug accountability records.

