¹ Visit 1 and Visit 2 may be combined into one visit. On the day of screening procedures, if preliminary entry criteria indicate that the subject is probably eligible, the eDiary can be issued and the subject may begin the run-in period. If during the run-in period, additional information becomes available to exclude the subject (e.g., return of 12-lead ECG or lab results), the subject should be notified of screen failure and instructed to return any provisional eDiary device (if applicable) to the center.

³ Physical exam to include (but not limited to) HEENT, Dermatologic, Neurological, General Appearance, Lymph Nodes, Cardiovascular, Respiratory, Gastrointestinal, and Musculoskeletal

⁴ Weight at each visit; both height and weight to be collected at screening and final visit only (or early termination visit)

⁵ Vital signs include temperature, respiratory rate (RR), blood pressure (BP), and heart rate (HR)

⁶ Clinically significant abnormal values may be repeated to confirm eligibility

⁷ Phone contacts monthly at months 4, 5, 7, 8, 10, and 11 to remind subjects to treat at least two migraine attacks per month and to assess for adverse events and concomitant medication use

⁸ Subjects may return for an unscheduled visit to pick up additional study medication as needed.

All study visits and procedures will be performed according to the Schedule of Study Procedures as listed in [Table 10](#). Subject visits should be scheduled as soon as possible within the specified windows.

Subjects must be fasting (i.e., nothing by mouth for at least 4 hours; drinking water during the 4-hour fast before clinical laboratory assessments is permitted) for all laboratory collections.

6.1.1 Screening (Visit 1): Up to 1 Week Prior to Start of the Run-in Period

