 - Subject reported skin assessment for bruising, swelling, and/or redness (at 30 minutes, 2 hours, 12 hours, 24 hours and 48 hours post patch administration time points only)
 - Subject reported skin pain and skin itching at 48 hours post patch administration
- Dispense the Subject Skin Grading Card (Appendix 4) with the eDiary and instruct the subject to refer to this card when grading their skin reaction(s)/symptom(s) in the eDiary. The Grading Card will include a subject reminder to contact the study physician if he/she experiences any serious or severe skin reaction(s) at any time point or for worsening or non-resolving reactions at approximately 3 days post patches application (at 72 hours). In addition, the eDiary will remind the subject to call the study physician if he/she experiences any skin reaction(s) and/or symptom(s) at the patch application site which worsens rather than improves over approximately a five-day period. If the subject

contacts the study physician at any time point for worsening or non-resolving reactions, the subject must be seen for an unscheduled visit. The skin reaction(s)/symptom(s) will be assessed, recorded as an adverse event in the eCRF and followed to resolution.

6.1.5 Month 1 (Visit 4), Month 2 (Visit 5), Month 3 (Visit 6), Month 6 (Visit 7)

Visits must be scheduled to occur on (or within ± 7 days) of the protocol specified study day, ie, on study days 28 (Month 1), 56 (Month 2), 84 (Month 3), and 168 (Month 6). The following procedures will be performed at each visit:

- Administer the Migraine Assessment of Current Therapy (Migraine-ACT) which is completed by the subject
- Collect any unused patches, perform accountability, and dispense patches with applicator
- Perform physical exam, (Month 6 only) (height does not need to be recorded)
- Record vital signs: temperature, respiratory rate (RR), blood pressure (BP), and heart rate (HR)
- Collect urine for urine pregnancy test for all WOCBP
- Collect urine for drug abuse testing (Month 6 only)
- Perform 12-lead electrocardiogram (ECG) (Month 6 only)
- Ensure subject is dispensed the Subject Skin Grading Card (to be used with eDiary entries).
- Collect and review subject's eDiary data with the subject for the following:
 - Subject compliance with study drug treatment and subject responses in eDiary

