- Perform Investigator Skin Assessment (presence of blisters, scaly or flakey skin, erosions or open sores, scarring, hyperpigmentation, bruising, redness, and/or swelling) of upper arm where patches have been applied
- Any cutaneous signs or symptoms found on the investigator skin assessment will be recorded as an adverse event on the eCRF and followed to resolution.
- Record concomitant medications
- Record adverse events. In addition, any skin reaction(s) entered into the eDiary by the subject must also be recorded as an adverse event in the eCRF and followed to resolution.

6.1.6 Month 9 (Visit 8) and Month 12 End of Study Final Visit (Visit 9/or Early Termination)

The Month 9 and 12 visits are to be scheduled on (or within ± 7 days) of the protocol specified study day, i.e., on study days 252 (Month 9) and 336 (Month 12). The following procedures will be performed. If a subject terminates early from the study at any time after applying M207, an Early Termination visit must be scheduled to occur within 7-14 days after the subject's last patch application.

- Administer the Migraine Assessment of Current Therapy (Migraine-ACT) to be completed by the subject
- Collect the applicator, any unused patches, and perform accountability
- Dispense M207 patches (Month 9 only)
- Perform physical exam, including weight and height (Month 12 final visit/or early termination only)
- Record vital signs: temperature, respiratory rate (RR), blood pressure (BP), and heart rate (HR)
- Collect blood (4-hr fasting) for clinical laboratory measurements including clinical chemistries and hematology (Month 12 final visit/or early termination only)
- Collect urine for urine pregnancy test for all WOCBP
- Perform 12-lead electrocardiogram (ECG) (Month 12 final visit/or early termination only)
- Ensure subject is dispensed a Subject Skin Grading Card (at Month 9 only)
- Collect and review subject's eDiary data with the subject for the following:
 - Subject compliance with study drug treatment and subject responses in eDiary
- Perform Investigator Skin Assessment (presence of blisters, scaly or flakey skin, erosions or open sores, scarring, hyperpigmentation, bruising, redness, and/or swelling) of upper arm where patches have been applied
- Any cutaneous signs or symptoms found on the investigator skin assessment will be recorded as an adverse event on the eCRF and followed to resolution.
- Record concomitant medications

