- Record adverse events. In addition, any skin reaction(s) entered into the eDiary by the subject must also be recorded as an adverse event in the eCRF and followed to resolution.

6.1.7 Monthly Phone Contacts at Months 4, 5, 7, 8, 10, and 11 (\pm 7 days)

Contact subject each month to assess for adverse events, collect and record concomitant medications and remind subject to continue to treat a minimum of 2 qualifying migraine attacks per month.

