8 ADVERSE EVENTS

All systemic and cutaneous AEs, regardless of suspected causal relationship to the investigational products, will be reported as described in the following sections. Subject reported bruising, bleeding, erythema, edema, skin itching and skin pain are collected through the eDiary and will also be recorded as adverse events in the eCRF and followed to resolution.

For all systemic and cutaneous AEs, the investigator must obtain adequate information both to determine the outcome of the AE and to assess whether it meets the criteria for classification as a SAE (see [Section 8.2.1.1](#)) requiring immediate notification (within 24 hours) to the Medical Monitor (MM) and Pharmacovigilance Group (PV) by completing a SAE Report Form. Sufficient information should also be obtained by the investigator to determine the causality of the AE, since he/she is required to assess causality. For systemic and cutaneous AEs with a causal relationship to the investigational product, including **all** application site reactions, investigator is required to follow-up until the event or its sequelae resolve or stabilize at a level acceptable to the investigator.

Pregnancy: In the event that a pregnancy occurs, it will not be considered an AE but requires notification within 24 hours of investigator awareness to the Medical Monitor and Pharmacovigilance Group by completing a Pregnancy Report Form. The investigator will follow the pregnancy and report the outcome. The subject will be discontinued from the study if she becomes pregnant anytime during the study.

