Study Drug Self-							→	

	VISIT 1 ¹ Screening	VISIT 2 ¹ Start of Run- In	VISIT 3	VISIT 4, 5, 6	VISIT 7	VISIT 8	VISIT 9 Final visit or ET	VISIT 10 Two Week Post Study Visit
Procedure	Up to 1 week prior to Run-in	Week -2 (up to -3)	Day 1 (dispense patches)	Month 1, 2, 3	Month 6	Month 9	Month 12	Two Week Safety visit
Administration								
Subject eDiary Reported Skin Assessments							→	
Migraine-ACT (subject completed)				X	X	X	X	
Investigator Skin Assessments				X	X	X	X	X
Monthly phone contacts to subject ⁷							→	
Collect Unused Patch(es)/Perform Drug Accountability ⁸				X	X	X	X	
Collect and Review eDiary data			X	X	X	X	X	
Record Adverse Events	X	X	X	X	X	X	X	X
Record Concomitant Medications	X	X	X	X	X	X	X	X

¹ Visit 1 and Visit 2 may be combined into one visit. On the day of screening procedures, if preliminary entry criteria indicate that the subject is probably eligible, the eDiary can be issued and the subject may begin the run-in period. If during the run-in period, additional information becomes available to exclude the subject (e.g., return of 12-lead ECG or lab results), the subject should be notified of screen failure and instructed to return any provisional eDiary device (if applicable) to the center.

³ Physical exam to include (but not limited to) HEENT, Dermatologic, Neurological, General Appearance, Lymph Nodes, Cardiovascular, Respiratory, Gastrointestinal, and Musculoskeletal

⁴ Weight at each visit; both height and weight to be collected at screening and final visit only (or early termination visit)

⁵ Vital signs include temperature, respiratory rate (RR), blood pressure (BP), and heart rate (HR)

⁶ Clinically significant abnormal values may be repeated to confirm eligibility

⁷ Phone contacts monthly at months 4, 5, 7, 8, 10, and 11 to remind subjects to treat at least two migraine attacks per month and to assess for adverse events and concomitant medication use

⁸ Subjects may return for an unscheduled visit to pick up additional study medication as needed.

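### After Month 3, scheduled pregnancy tests are 84 days apart and the six phone contacts in between list no pregnancy question: a low-priority safety improvement

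*Protocol*

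**What the plan says.** **Tests.** Protocol Table 10 lists a serum pregnancy test at screening. Urine tests follow at Day 1, Months 1, 2, 3, 6 and 9, and at Month 12 or early termination. Protocol 6.1.3, 6.1.5 and 6.1.6 repeat the urine tests and set the visits on Days 28, 56, 84, 168, 252 and 336, each with a 7-day window either side. SAP Table 1 carries the same schedule.

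**Calls.** Protocol 6.1.7 places contacts at Months 4, 5, 7, 8, 10 and 11 and gives their content: "Contact subject each month to assess for adverse events, collect and record concomitant medications and remind subject to continue to treat" at least two qualifying attacks per month. Table 10 footnote 7 agrees: "to remind subjects to treat at least two migraine attacks per month and to assess for adverse events and concomitant medication use". SAP Table 1 footnote 7 repeats it: "Phone contacts monthly at months 4, 5, 7, 8, 10, and 11 to remind subjects to treat at least two migraine attacks per month".

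**Pregnancy.** Protocol Section 8 states: "In the event that a pregnancy occurs, it will not be considered an AE but requires notification within 24 hours of investigator awareness". It then adds: "The subject will be discontinued from the study if she becomes pregnant anytime during the study". Protocol 3.2.6.1 also lists pregnancy, but among reasons for which a subject is permitted, not required, to be withdrawn.

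**Safeguards.** Inclusion criterion 5 requires contraception for the whole trial. Exclusion criterion 12 bars women who are pregnant or planning a pregnancy. Protocol 4.2 allows dispensing at a visit only "after it has been established that a subject continues to qualify for the study".

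**The concern.** The protocol means to avoid dosing in pregnancy: it excludes pregnant women and discontinues those who become pregnant. Both that rule and the 24-hour notification depend on someone finding out. From Month 3 the scheduled means of finding out becomes three times less frequent. The site still speaks to the subject monthly, but the listed content of the call does not include the question.

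The adverse-event enquiry is not a formal substitute, given Section 8. The eDiary questions in Appendix 3, which release each dose, contain no pregnancy item either. A subject with an unrecognised pregnancy could therefore follow the protocol in full and keep treating until the next quarterly test, with two calls in between reminding her to treat.

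What is at stake is avoidable exposure in individual subjects. Sample size, endpoint definitions and the descriptive analyses are not in question.

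**Working it through.** The plan states no testing interval, so there is no figure to reproduce. The intervals follow from the visit days.

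**Inputs.** Test days 28, 56, 84, 168, 252 and 336, each ±7 (Protocol 6.1.5, 6.1.6, Table 10). Calls at Months 4, 5, 7, 8, 10 and 11, ±7 days (Protocol 6.1.7). The documents give no study days for the calls; I assume 28-day months, which gives Days 112, 140, 196, 224, 280 and 308.

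**Gap between consecutive tests** = later day − earlier day. Maximum = (later day + 7) − (earlier day − 7).

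| Tests | Nominal gap (days) | Maximum gap (days) |
|---|---|---|
| Month 1 to 2, and 2 to 3 | 56 − 28 = 28; 84 − 56 = 28 | (56 + 7) − (28 − 7) = 42 |
| Month 3 to 6 | 168 − 84 = 84 | (168 + 7) − (84 − 7) = 98 |
| Month 6 to 9 | 252 − 168 = 84 | 98 |
| Month 9 to 12 | 336 − 252 = 84 | 98 |

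**Share of treatment time in the long gaps.** For a 12-month stay: (336 − 84)/336 = 75%. For a six-month stay: (168 − 84)/168 = 50%. This is time between tests, not time exposed in pregnancy.

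**Illustration of dosing in one gap.** I assume 2 treated attacks per 28 days (the reminded minimum) to 8 (the eligibility maximum). Over 84 days, which is three 28-day periods, that is 2 × 3 = 6 to 8 × 3 = 24 doses. To count all of these as exposure in pregnancy, conception must fall at the start of the gap and go unnoticed for 12 weeks. If conception is instead assumed uniform over the gap, the mean time to the next test is 84/2 = 42 days, or 3 to 12 doses. A subject who notices and reports stops earlier still.

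**Does a dispensing step have to fall in the gap?** Six doses are 12 patches. A refill kit holds 8, so two kits (16 patches, 8 doses) given at Month 3 are enough at 2 attacks per month, and Protocol 4.2 sets no cap on kits. A resupply visit inside the gap is therefore possible but not assured, and no pregnancy test is listed for unscheduled visits.

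**With a question at each call.** The nominal interval between checks of either kind (a test or a question) becomes 112 − 84 = 28 days, at most (112 + 7) − (84 − 7) = 42. This matches the spacing before Month 3, although a question is a weaker check than a test.

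**The case against.** The strongest reply is that the interval is a design choice. No document states an adequate interval, a fetal risk, a pregnancy rate or the number of WOCBP. The longer gap simply follows the visit schedule: every scheduled visit at which patches are dispensed includes a urine test, so no scheduled supply goes out untested. Contraception and the bar on planned pregnancy lower the risk further. All of this stands, and it sets the low priority.

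A second reply is that 6.1.7 summarises the call and is not a script. The call script and consent form were not available for review and may already ask about pregnancy. A subject may also volunteer it, or reveal it through a reported symptom or a new medication. That stands too. If the script does ask, 6.1.7 should say so.

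Three stronger readings are tempting. A reader might infer that the plan breaches a required testing frequency; none is set. A reader might infer that monthly home testing is needed; the documents give no basis for preferring it to the present tests plus a question. A reader might infer a material number of exposed pregnancies; without a WOCBP count or a rate, no expected number can be given.

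The difference between 3.2.6.1 and Section 8 can fairly be called editorial, because Section 8 is the specific rule. It is still worth correcting, since a site reading 3.2.6.1 alone would take discontinuation as optional.

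**Conclusion.** The point holds as a low-priority improvement in subject safety. After Month 3 the scheduled test interval triples from 28 to 84 days (98 at the window limits), and the six calls already in those gaps list no pregnancy item. The adverse-event enquiry does not formally fill the gap. No stated standard is breached and no statistical conclusion changes.

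The interval figures rest only on the visit days and windows in the protocol. The dosing illustration rests on the assumed attack rate and conception timing, and should not be read as an estimate of exposure. The conclusion about the calls rests on their listed content; the unseen script could remove it.

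**What to change.** 1. In Protocol 6.1.7, Table 10 footnote 7 and SAP Table 1 footnote 7, add for WOCBP: *Ask about a missed period or possible pregnancy. If suspected, the subject stops applying patches and returns for a pregnancy test, with serum confirmation if positive. Patches restart only if the result is negative.*
2. Extend Protocol Table 11 footnote 1 so that serum confirmation also applies to a test prompted by a phone contact.
3. In Protocol 3.2.6.1, take pregnancy out of the permissive list and state separately: *A subject who becomes pregnant must stop study drug and will be discontinued (see Section 8).*

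**Cost.** One field on the call form, an occasional unscheduled test, and short amendments to the sections named. During a hold the eDiary would still tell the subject to apply patches for a qualifying migraine, so the caller must say clearly that the hold overrides it. Brief holds may slightly lower the compliance figures in SAP 11.1 (at least 2 treated migraines per 30-day month) for the subjects affected. Endpoint definitions and sample size are unchanged.

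**Limit.** The question finds only pregnancies that the subject already suspects or that show as a missed period.

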6.1.8 Two Week Post Study Safety Visit (Visit 10)

This visit will occur 14-28 days after the End of Study Final Visit (or Early Termination visit). The following procedures will be performed:

- Record vital signs: temperature, respiratory rate (RR), blood pressure (BP), and heart rate (HR)
- Perform Investigator Skin Assessment (presence of blisters, scaly or flakey skin, erosions or open sores, scarring, hyperpigmentation, bruising, redness, and/or swelling) of upper arm(s) where patches have been applied
- Any cutaneous signs or symptoms found on the investigator skin assessment will be recorded as an adverse event on the eCRF and followed to resolution.
- Record concomitant medications

Record adverse events

6.2 Study Procedures

6.2.1 Informed Consent

Each study participant (or legally authorized representative) will be required to read, sign, and date the current institutional review board/independent ethics committee (IRB/IEC) approved version of the ICF. The consent process should also be documented in the study site's source documents. Informed consent must be obtained prior to performing any study-specific procedures. Both the participant and the study staff member who participated in the consent discussion with the participant must sign and date the ICF. Each study participant will be given a copy of the ICF. All participants will have an opportunity to ask questions before signing the ICF, and the study staff member who obtains consent will probe the subject to ascertain understanding of the elements of consent.

6.2.2 Inclusion/Exclusion Criteria

All inclusion criteria and eligibility criteria for subject treatment, and none of the exclusion criteria must be satisfied prior to assignment of a CTM kit to the subject and the start of study drug dosing.

6.2.3 Medical History and Demographics

Demographic information and a medical history, including history of menopausal status, will be obtained during screening. The medical history should include all current conditions, allergies, including recent illnesses and relevant past medical history. Subjects will be asked about current use of illicit drugs or alcohol. Information will also be obtained on the subject's history of migraine therapy. The Fitzpatrick Skin Type Questionnaire scale ([Appendix 1](#)) will also be administered at screening to document the subject's skin type.

6.2.4 Randomization

Not applicable.

6.2.5 Migraine Assessment of Current Therapy (Migraine-ACT)

See [Appendix 2](#) for the Migraine Assessment of Current Therapy (Migraine-ACT). This subject completed questionnaire will be administered at each clinic visit starting at Month 1.

6.2.6 Physical Examination

A physical exam will include, but is not limited to, HEENT, dermatologic, brief neurological, general appearance, lymph nodes, cardiovascular, respiratory, gastrointestinal, and musculoskeletal examinations.

6.2.7 Height and Weight

Subjects will have height measured only at the screening and the final visit (or early termination visit). Weight will be collected at screening, Day 1, Month 1, 2, 3, 6, Month 9 and Month 12, the final visit (or early termination visit). The subject must not wear shoes during the height measurement.

The subject should wear light clothing and no shoes during weight measurements. Subjects should be weighed on the same clinic scale during this study.

6.2.8 Vital Signs

All subjects will have vital signs (temperature, RR, BP, and HR) measured at screening and all subsequent visits.

Whenever possible, vital sign measurements will be taken before any blood samples are taken.

